06 AUGUST 2020, VERSION: 4.0

Adverse events

China AE reporting: Neuwave China AE [contact]

Global AE reporting: [contact]

Medical device complaints

Local CHU reporting: [contact]

Global CHU reporting: [contact]

Confidential Page 52 of 61

15. DEVIATION FROM CLINICAL TRIAL PROTOCOL AND REGULATIONS FOR CLINICAL TRIAL PROTOCOL AMENDMENT

The study protocol deviations are defined as the circumstances that fail to comply with the requirements of clinical trial protocol intentionally or unintentionally.

All protocol deviations should be reported as protocol deviations to the Sponsor via the study EDC database. The reporting should include the date and reason for protocol deviations. The investigator should also report the protocol deviations to the EC and all related department according to each site's requirements and in combination with the requirements and procedures of the EC.

If a protocol amendment occurs, the Sponsor or designated person should submit a summary of changes of the study protocol to the investigator, regulatory authority, and the Ethics Committee, etc. according to the relevant laws and regulations. All major amendments must be approved by the Ethics Committee and regulatory authority (if needed) prior to implementing any changes to study procedures.

If an amendment likely has major impact on the following items, this amendment belongs to the major amendment:

- Safety or physical or mental health of patients;
- Scientific value of trial;
- Implementation or management of trial;
- Quality or safety of investigational medical device specified in the trial.

16. DIRECT ACCESS TO SOURCE DATA AND DOCUMENT

The source data is defined as all information in the original record and its approved copy regarding the clinical findings, observations and other activities in the clinical trial, which can be used for reproduction and evaluation of clinical trial. The source documents are documents on which the source data is recorded, including printed, paper or electronic documents.

The patient's medical record and other study related documents (source documents) must be maintained and retained by the investigator. The investigator should allow the monitors and auditors/inspectors to review all relevant patient records, including but not limited to the following information:

- Medical/physical condition of the study patient that meets the inclusion criteria prior to participating this study;
- Process of informed consent;
- Operational description of use and implantation of the study product;

Confidential Page 53 of 61

- All inspection results and follow-up;
- Examined printed output file or report (for example, X-ray film) that is dated and signed;
- Description of AE and follow-up of AE (description of event, severity, date of occurrence, duration, correlation with the study device, study procedure, outcome, and treatment of the AE, concomitant medications when the AE occurs);
- Description of device complaint;
- Study patient's status at the end of the study or withdrawn from the study.

Appropriate source documents must be available for reviewing during the monitoring visit. The Sponsor expects that the study coordinator and/or investigator will also be available for questions during monitoring visits.

Those patients that specifically consent to the additional research analysis will have relevant patient characteristics, treatment and outcome data, that is already being captured for this study, compiled with the same type of data from consenting patients from other NeuWave Medical studies used in a separate analysis. These data will be collectively used for Time and Power predictive analytics and reported in an aggregate fashion. Patient/patient identifiable information will not be used except for the patient's study number. The goal of this analysis is to characterize the optimal MW ablation parameters for specific tumor types, locations, and liver conditions.

17. FINANCES AND INSURANCE

See the relevant study contract and insurance document.

18. CONFIDENTIALITY

The personal data of the patient participating in the trial is confidential; however, the Ethics Committee, NMPA, competent department of health and family planning, or the Sponsor and its authorized representative may review the personal data of the patient participating in the trial for the purpose of their work according to the local established procedure.

The personal data of the patient should be kept confidential during the entire period of clinical trial, and it should be ensured that the source data can be verified through the supporting information. A unique patient ID number (site number and patient number) will be used to identify all data for every enrolled patient. So long as the data is kept strictly confidential and that the privacy of the patient is ensured to be protected, the data related to this study may be available to third parties (for example, under the audit of regulatory authority).

Confidential Page 54 of 61

19. AGREEMENT ON THE PUBLICATION OF TRIAL RESULTS

Following completion of this study, an article might be prepared and published in a scientific journal. No major results or experience from any individual site in this study can be published before the multicenter trial results are prepared and published. An exception to this rule will need prior approval from the Sponsor. A second publication may be generated by corresponding principal authors. The final analysis and review from all trial data are required to be reviewed and approved by the Sponsor.

20. RESPONSIBILITIES THAT EACH PARTY SHOULD BEAR

20.1. Responsibilities of the Sponsor

- 1) The Sponsor is responsible for the initiation, application, organization and monitoring of clinical trial.
- 2) The Sponsor is responsible for the organization to establish and modify the investigator's brochure, clinical trial protocol, informed consent form, Case Report Form, relevant standard operating procedure and other relevant documents, carry out the training required for the clinical trial, and provide these documents to the investigators before the study starts.
- 3) The Sponsor should select the qualified trial institution and investigators.
- 4) The Sponsor should sign a written agreement with the clinical trial institution and the investigator regarding the clinical trial.
- 5) The Sponsor should provide qualified study product according to the regulatory requirements. The Sponsor should be responsible for the safety of investigational medical device in the clinical trial. The AE, SAE, and the device complaint that may cause an SAE should be collected and reported in accordance with the provisions.
- 6) The Sponsor should inform the regulatory authority at every level when the Sponsor decides to suspend or terminate the clinical trial or at the end of the study.
- 7) The Sponsor should ensure the investigator conducts the study strictly in compliance with the clinical trial protocol, corrects the protocol deviations in a timely way, and reserves the rights to report, to the regulatory authority, any of issues related to this.
- 8) The Sponsor should bear the treatment cost and relevant economic compensation for the clinical trial-related injury or death of patients, except for damages due to the fault of medical institution and medical staff in the diagnosis and treatment.
- 9) The Sponsor should select qualified monitors for monitoring and organizing any inspections, as appropriate.

Confidential Page 55 of 61

20.2. Responsibilities of Clinical Trial Institution and Investigator

- The clinical trial institution should evaluate the relevant resources according to the features of investigational medical device prior to the clinical trial, to decide whether to participate in this clinical trial.
- 2) The clinical trial institution should properly keep the records and documents of clinical trial according to the agreement with the Sponsor.
- 3) Make sure that the investigators responsible for the clinical trial have the qualification in accordance with the requirements of related laws and regulations.
- 4) The administrative department for clinical trial of medical device of clinical trial institution should cooperate with the Sponsor to apply to the Ethics Committee and submit the relevant documents prior to the clinical trial according to requirements.
- 5) The investigator should ensure that the relevant workers participating in the trial have the enough resources and proper training and keep the training related documents.
- 6) The investigator should ensure to use the investigational medical device only for the patients of this clinical trial.
- 7) The investigator may not charge patients any fees for participating in the study.
- 8) The investigator should strictly follow the clinical trial protocol, with the exception of emergency circumstances when the patient faces the direct risk and needs immediate clinical measures, which can be reported later in a written form.
- 9) The investigator is responsible for recruiting the patients, communicating with the patient or its legal representative before signing the informed consent.
- 10) The investigator should protect the rights, safety and health of the patients.
- 11) In case of an AE occurring in the clinical trial, the investigator should protect the safety of the patients and timely report the event to the regulatory authority.
- 12) The investigator should record all AEs occurring and device deficiencies found in the process of clinical trial, work with the Sponsor to analyze the causes of the events, generate the written analysis report, present the comments on the continuation, discontinuation or termination of the trial, and report to the Ethics Committee by the administrative department for clinical trial of medical device of clinical trial institution for review.
- 13) The investigator should make sure that the clinical trial data is accurately, completely, clearly and timely recorded in the Case Report Form.
- 14) The clinical trial institution and investigator should make sure that the data, documents and records generated in the clinical trial are timely, true, accurate, clear, and attributable.
- 15) The clinical trial institution and investigator should accept and cooperate with the

Confidential Page 56 of 61

monitoring and audit of the Sponsor, the supervision of the Ethics Committee, and the inspection of the Food and Drug Administration, competent department of health and family planning, etc., and provide all required records related to the trial.

- 16) If the clinical trial needs to be suspended or terminated, the patients should be informed accordingly. It should be ensured that the patients receive the proper care and follow-up. The clinical trial institution and investigator should also report this in accordance with the regulations and provide a detailed written explanation. The relevant report should be submitted to the local Food and Drug Administration at the provincial, autonomous regional and municipal level, if necessary.
- 17) The clinical trial institution and investigator reserve the rights to report to the regulatory authority at every level when the Sponsor violates relevant laws and regulations.
- 18) The investigator should complete all records and reports at the end of clinical trial. The investigator should also ensure that the received investigational medical devices are properly handled and recorded according to the requirements.

APPENDIX 1: STUDY DEVICES CODE LIST

Model	Description
NWC2CN1N	NeuWave Certus™ Microwave Ablation System
CTBKT1	CT Bed Rail PDM Mounting Bracket, Standard (GE, Philips)
CTBKT2	CT Bed Rail PDM Mounting Bracket, D68 X W585 Standard (Siemens)
CTBKT3	CT Bed Rail PDM Mounting Bracket, D48 X W656 Standard (Toshiba)
CTBKT4	CT Bed Rail PDM Mounting Bracket, D88 X W645 (Siemens Alt)
CTBKT5	CT Bed Rail Mount, Flat
PDM1TBL	Table PDM Mount
PD2MSURG	CT Bed Rail PDM Mounting Bracket, 18: Long (Surgical Mount)
LK15CN	NEUWAVE CERTUS LK Probe 15CM 17ga
LK20CN	NEUWAVE CERTUS LK Probe 20CM 17ga
LK15XTCN	NEUWAVE CERTUS LK XT Probe 15CM 15ga
LK20XTCN	NEUWAVE CERTUS LK XT Probe 20CM 15ga
PR15CN	NEUWAVE CERTUS PR Probe 15CM 17ga
PR20CN	NEUWAVE CERTUS PR Probe 20CM 17ga
PR15XTCN	NEUWAVE CERTUS PR XT Probe 15CM 15ga
PR20XTCN	NEUWAVE CERTUS PR XT Probe 20CM 15ga
NWSR25CN	NEUWAVE CERTUS SR Probe 25CM 13ga

Note: These are collectively described as "study devices."

Confidential Page 59 of 61

The second interim analysis will occur after all enrolled patients have completed the 12-month visit and will include a summary of local tumor progression rates as well	;
as safety through one year	27
8.7 Handling of Missing Data	27
8.8 Adjustments for Multiplicity	27
8.9 Subgroup Analysis	27
8.10 Assessment of Site Homogeneity	28

9	Data Monitoring (Committee (I	DMC)	28
---	-------------------	--------------	------	----

1 Study Design

This is a single-arm, prospective, multicenter study. Individuals who are assessed for NeuWave Certus Microwave (MW) ablation of hepatocellular carcinoma (HCC) in accordance with their institution's standard of care, who meet study entry criteria, and sign the informed consent will be enrolled. The subjects will be treated with MW ablation and will be followed for up to 36 months after the ablation procedure to assess safety and ablation outcomes.

The total sample size will be 137 subjects. To provide sites with an opportunity to get equal experience in the use of the Certus system, there will be 3 patients per site treated as part of a run-in phase. There will be 4 sites participating in the study. Therefore, 12 of the 137 subjects will be included in the run-in phase.

2 Treatment Assignment

All subjects enrolled will undergo microwave ablation of HCC using only the NeuWave Certus Microwave Ablation System.

3 Randomization and Blinding Procedures

This is a single-arm study. Hence, there will be no control or comparison group. Therefore, there is no need for randomization or blinding.

4 Visit Schedule / Interval Windows

Visit Number	Visit Label for Statistical Outputs	Visit Name	Study Phase	Visit Name (Visit Window)
1	Visit 1	Screening	Screening	Screening (within 14 days before ablation)
2.1	Visit 2A	Day 0	Ablation	Ablation (day 0)
2.2	Visit 2B	Post- Ablation	Post-Ablation	Post-Ablation (0 to 7 days)
3	Visit 3	Month 1		1 months (± 7 days) post-ablation
4	Visit 4	Month 3		3 months (± 7 days) post-ablation
5	Visit 5	Month 6		6 months (± 14 days) post-ablation
6	Visit 6	Month 9		9 months (± 14 days) post-ablation
7	Visit 7	Month 12	Follow-up	12 months (± 14 days) post-ablation
8	Visit 8	Month 18		18 months (± 28 days) post-ablation
9	Visit 9	Month 24		24 months (± 28 days) post-ablation
10	Visit 10	Month 30		30 months (± 28 days) post-ablation
11	Visit 11	Month 36		36 months (± 28 days) post-ablation
XX.X	USV	Unsheduled		Unscheduled Visit

Table 1: Study Timepoint

The visit in the outputs should be derived based on the above visit schedule.

If a visit is performed "out of window" (i.e.between two visit windows), the visit should be analyzed as part of the the visit closest in terms of time or number of days as outlined by visit schedule, above. More details can be found in Table 1 of the protocol.

In case any retest performed within one visit, the visit in the outputs will be derived based on the above time windows. The visit with worst result will be used as the planned visit.

5 Levels of Significance

Given that no hypotheses are formally being tested in this study, no levels of significance are specified. Estimation of specified study endpoints will be performed using two-sided 95% confidence intervals (CI).

6 Analysis Sets

6.1 All Subjects Screened Set (SCR)

The All Subjects Screened Set (SCR) contains all subjects who provide informed consent for this study. The SCR will be used for disposition of study subjects.

6.2 Full Analysis Set (FAS)

The Full Analysis Set (FAS) contains all subjects who are enrolled in the study, are not part of the run-in phase, and have the NeuWave Microwave Ablation System used for ablation. The FAS will be used for effectiveness endpoints and safety analysis.

Enrolled subjects means subjects who meet study entry criteria and sign the informed consent.

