8. STATISTICAL CONSIDERATIONS

8.1. Statistical Design, Method and Analysis Procedure

This is a single-arm, prospective, multicenter study designed to evaluate the efficacy and safety of the NeuWave Certus Microwave Ablation System in the treatment of Chinese patients

Confidential Page 40 of 61

who have a single HCC tumor up to 5 cm or who have a maximum of 3 HCC tumors of up to 3 cm per tumor.

Categorical variables will be summarized descriptively by frequencies and associated percentages. Continuous variables will be summarized descriptively by number of patients, mean, standard deviation, median, minimum, and maximum. Confidence intervals will also be provided for procedure-related variables. A detailed Statistical Analysis Plan (SAP) describing all planned analyses of data collected in this study will be finalized prior to any analysis of data.

There will be three analysis populations defined for summary of data collected in this study. The primary analysis of safety and effectiveness endpoints will be performed on the Full Analysis Set, defined as all patients who are enrolled in the study, are not part of the run-in phase, and have the NeuWave Microwave Ablation System used for ablation. A Per Protocol analysis set will be defined as all patients in the Full Analysis Set who have no major protocol deviations. Effectiveness analyses will be repeated for the Per Protocol Set. The Safety Set will include all patients who provide informed consent and have MW ablation attempted with the NeuWave system and includes run-in phase patients. The Safety Set will be used for summarization of safety endpoints only. Safety and effectiveness data collected on patients participating in the run-in phase may be summarized separately from the remaining patients. There will be at least one planned subgroup analysis based on whether or not patients have a repeat ablation in the first 30 days to correct a margin (A1 to A0). A summary of all efficacy endpoints as well as adverse event summaries will be provided for all patients who only have the initial, planned ablation procedure at Visit 2A. These summaries will also be provided for all patients who receive a repeat ablation in the first 30 days.

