8.5. Criteria and Reason for Terminating the Trial based on the Statistical Results

There are no planned analyses whose intent would be to stop the study early due to futility or superiority.

8.6. Statistical Method of All Data, together with the Handling Method of Missing, Unused and Error Data (including Termination and Withdrawal Halfway) and Unreasonable Data

All analyses will be performed only on patients undergoing ablation with the NeuWave Microwave Ablation System and only observed data will be analyzed. There will be no imputation of missing data for any parameters or for early terminated patients. At a given interim analysis time point, if a patient has not discontinued from the study, then the patient will be considered censored as of the date of the interim database lock for that analysis unless they have had an occurrence of the given endpoint prior to that interim database lock date. For time to event endpoints in the final analysis of data, patients who have not experienced an event will be considered censored at the last known visit date.

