6.4 Safety Analysis Set (SAF)

The Safety Analysis Set (SAF) contains all subjects who provide informed consent and have MW ablation attempted with the NeuWave system and includes run-in phase subjects. The Safety Set will be used for summarization of safety endpoints only.

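### As worded, the Full Analysis Set omits main-phase subjects whose ablation was attempted but abandoned before any energy was delivered, so Technical Success and Technical Efficacy can only be biased upward.

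*SAP*

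**What the plan says.** Protocol 8.1 defines both sets in one paragraph. FAS members "are not part of the run-in phase, and have the NeuWave Microwave Ablation System used for ablation"; the Safety Set requires only that ablation was attempted. The SAP repeats the contrast:

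- **SAP 6.2 (FAS):** subjects must "have the NeuWave Microwave Ablation System used for ablation". On purpose: "The FAS will be used for effectiveness endpoints and safety analysis". On enrolment: "Enrolled subjects means subjects who meet study entry criteria and sign the informed consent", so enrolment alone does not imply that the device was used.
- **SAP 6.4 (Safety Set):** subjects must "have MW ablation attempted with the NeuWave system and includes run-in phase subjects". On purpose: "The Safety Set will be used for summarization of safety endpoints only".
- **SAP 6.3 and 8.4.1:** effectiveness endpoints are summarized on the FAS and the Per Protocol Set (PPS), which is a subset of the FAS. Subject-level Technical Success and Technical Efficacy divide by all subjects in the FAS or PPS. Tumor-level Technical Success divides by the target lesions that were evaluable at Visit 2B, and tumor-level Technical Efficacy follows the same method.
- **Protocol 8.6:** "All analyses will be performed only on patients undergoing ablation with the NeuWave Microwave Ablation System", using observed data and no imputation.

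Neither document defines *used*, *attempted* or *undergoing*. Neither says how an attempted but undelivered ablation is scored.

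**The concern.** In a device study, failing to deliver the treatment is a technical failure. A probe fault or an unreachable target before any energy is applied would place a main-phase subject in the Safety Set. On the plain wording that subject is outside the FAS, and so outside the PPS too. Only non-successes can be lost this way, so any resulting bias has one direction.

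The estimates carry the weight of the study. Protocol 4.3 says the trial is meant to support registration in China. There is no control arm, hypothesis or acceptance threshold, and Protocol 8.4 judges performance from the data as a whole, set beside other HCC therapies. A success rate calculated without undelivered attempts could compare too favorably with rates that include them.

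**Working it through.** **1. The plan's own numbers.** 100 subjects with one-year data and 20% dropout give 100/(1 − 0.20) = 125 main-phase subjects. Adding 3 × 4 = 12 run-in subjects gives 137. Both match Protocol 8.2.1 and SAP 7. Protocol 7.1.5 does not replace withdrawn patients, so abandoned cases come out of the 125 and are not added to it.

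**2. Who is affected.**

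| Main-phase subject | Safety Set | FAS | Subject-level Technical Success |
|---|---|---|---|
| Attempt abandoned, no energy delivered | in | out, on plain wording | not counted |
| Energy delivered, then stopped | in | in (device arguably used) | non-success unless all tumors are A0 or A1 |
| Ablation completed | in | in | scored on A0/A1/A2 |

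Only the first row is at issue. The protocol allows that state to occur. Section 7.2.3 requires a probe to pass a functional test before it can ablate, section 7.2.4 records placement attempts separately from ablations, and section 14.3 lists device malfunction among possible complaints.

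**3. Size at subject level.** Let 125 main-phase subjects be attempted, k of them abandoned before energy delivery, and x be successes.

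- As written: x/(125 − k)
- All attempts counted: x/125
- Difference: x/(125 − k) − x/125 = [x/(125 − k)] × k/125

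Per case this is the FAS success rate divided by 125: 91.6/125 = 0.73 points, or 97.1/125 = 0.78 points.

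The success rates are assumptions taken from the protocol's background. The 91.6% (98/107) comes from the retrospective series with this device. The 97.1% is printed for the large Chinese multicenter series; its printed fraction, 1276/1363, equals 93.6%, which lies inside the range. Both have tumor denominators and are applied here to subjects for illustration. No abort rate is given, so k is also an assumption. x is the rate times (125 − k), rounded. Intervals are two-sided 95% Wald, as in SAP 8.4.1, capped at 100.

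| Assumed rate | k | FAS as written | All attempts | Fall (points) |
|---|---|---|---|---|
| 91.6% | 1 | 114/124 = 91.9% (87.1 to 96.7) | 114/125 = 91.2% (86.2 to 96.2) | 0.7 |
| 91.6% | 3 | 112/122 = 91.8% (86.9 to 96.7) | 112/125 = 89.6% (84.2 to 95.0) | 2.2 |
| 91.6% | 6 | 109/119 = 91.6% (86.6 to 96.6) | 109/125 = 87.2% (81.3 to 93.1) | 4.4 |
| 97.1% | 1 | 120/124 = 96.8% (93.7 to 99.9) | 120/125 = 96.0% (92.6 to 99.4) | 0.8 |
| 97.1% | 3 | 118/122 = 96.7% (93.6 to 99.9) | 118/125 = 94.4% (90.4 to 98.4) | 2.3 |
| 97.1% | 6 | 116/119 = 97.5% (94.7 to 100) | 116/125 = 92.8% (88.3 to 97.3) | 4.7 |

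At k = 0 the two columns agree.

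**4. Tumor level.** A tumor that received no energy has no ablation zone to grade at Visit 2B, so it also drops out of the evaluable-lesion denominator. Changing the FAS wording alone would not bring it back.

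**The case against.** **The words may be loose synonyms.** Protocol 8.6 confines all analyses, safety included, to patients undergoing ablation. If the terms are strictly distinct, that rule conflicts with a Safety Set built on attempts; if they are synonyms, the conflict goes and the FAS already holds attempted cases. This reading is possible. But Protocol 8.1 chooses different words for two sets in the same paragraph, and the SAP keeps the difference. If one meaning was intended, saying so costs nothing.

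**The exclusion would be visible.** SAP 8.2 tabulates treated and discontinued subjects and presents the analysis sets. Main-phase attempts outside the FAS could be found as the Safety Set minus the run-in set minus the FAS. This is right, and it rules out any suggestion of concealment. It does not correct the reported rate.

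**Redefining the FAS would create new gaps.** This stands. SAP 8.1.1 sets the reference date at the first ablation, and LTP, PFS and OS all run from it. A subject never ablated has no time zero, so *attempted* should not simply replace *used* for every endpoint.

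**No decision can flip.** Also true: nothing is tested and no threshold is set. The point concerns the estimate and its interval, not error rates or sample size.

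A reader might infer that every interrupted or incomplete procedure escapes the denominator. The documents do not support that. Once energy is delivered the device has arguably been used, the subject stays in the FAS, and incomplete ablation is graded A2, which is not a success.

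**Conclusion.** The point holds for attempts abandoned before any energy is delivered. On the plain wording these subjects are in the Safety Set but in no effectiveness denominator, so subject-level Technical Success and Technical Efficacy can only be too high as a result. The tumor-level rates share the gap through their evaluable-lesion denominator.

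The direction is certain whenever such a case occurs. The size is not known: about 0.7 to 0.8 points per case at subject level, given 125 attempts and success rates of about 92% to 97%, all assumed. A reader might infer that the reported rate will be materially inflated, but the documents give no abort rate, and with no such cases nothing changes. The planned 125 and 137 are unaffected.

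**What to change.** - For Technical Success and Technical Efficacy only, use as denominator all enrolled non-run-in subjects, and their target tumors, in whom ablation with the NeuWave system was attempted.
- Count an attempted but undelivered ablation as non-success for both endpoints, at subject and tumor level. State this in the tumor-level denominator in SAP 8.4.1.
- Define *used* and *attempted*, and say how a subject is classed if an abandoned attempt is followed by a completed session.
- Report the number of undelivered attempts with reasons, for example in the disposition table of SAP 8.2.
- Keep LTP, PFS and OS on ablated subjects, whose time zero is the ablation.
- Align Protocol 8.1 and 8.6 with SAP 6.2 and 8.4.1.

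The cost is a few sentences across the two documents and one line in the disposition table, with no change to sample size. The reported rates may be slightly less favorable.
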